Buffalo: The Buffalo pediatric asthma service ([name], co-I) that will be used for enrollment is a three-site practice with a diverse patient demographic. The main clinic site is an inner-city clinic attached to the Women and Children's Hospital of Buffalo. In addition, there is a suburban satellite clinic and a suburban/rural satellite clinic. The Buffalo pediatric asthma service has 1160 patients in the age range proposed for the study and 315 new patients in this age range each year. Given these numbers, if 26% of caregivers have current MDD (as in our pilot study), then over a 4 year enrollment period the site will have 547 eligible participants. To enroll 98 participants, 18% of these will need to agree to participate.

Participant retention: We will use established methods for recruiting and retaining populations over long periods of time. Drs. [name] and [name] have used these methods throughout their multi-visit studies and obtained excellent retention statistics (95% completion of a 6 week study). [name] (PI) was an investigator on TMAP, a large multisite study using treatment algorithms for one year in patients with psychiatric illnesses in a similar fashion as the proposed study. In the MDD module of TMAP, retention was 100% at 3 months, 99.5% at 6 months, 83.2% at 9 months and 75.9% at 12 months. To maximize retention in the proposed study, multiple contact numbers (home, cell, work, family, friends), mailing addresses, and e-mail addresses will be obtained. Participants will be compensated appropriately for participation, transportation, time, and effort. Participants will have contact with research staff every 2-4 weeks either by phone or in person to keep them engaged in treatment. Participants are in the study for 52 weeks even if they miss some appointments, and we will collect as much data from each participant as possible. It is noteworthy that our data analytic procedures have robust methods of dealing with missing data. In addition, we propose enrolling 196 participants, rather than the 175 needed based on a power analysis, to allow for some early attrition.

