3.3.c.iii. Medication: Caregivers with current MDD will be offered antidepressant treatment from a research psychiatrist at no cost for 52 weeks. All medications used will be FDA-approved for MDD. The antidepressants and augmenting agents selected are widely used. We will provide these to the participants at each visit. This method of dispensing medications is different than in clinical practice where a patient would receive the medication at a pharmacy. We propose to use this method to enhance medication adherence and optimize internal validity of the study. Adherence to medication will be assessed by pill counts. We will use a simplified version of the TMAP MDD algorithm that has been adapted for this study. The algorithm is flexible because participants will potentially enter the study with different treatment histories. The doses of antidepressant will be titrated upward, to the FDA-approved maximum if needed, with the goal of achieving depression remission or full response. If the participant is already taking an antidepressant, they will remain on the prescribed medication until the first evaluation stage required by the algorithm and the doctor will assess how well the medication is working at that stage. If this is the first depressive episode and during the course of the study the participant's depression symptoms improve to the point at which they may no longer require medication, the doctor can evaluate if subject should be tapered off the medication. This would only be after at least 6 months of full remission of symptoms. At any time, the subject is free to decide to discontinue taking medication but can remain in the study under the study doctor's care. This decision will be fully discussed with the study doctor for safety reasons. After 12 weeks a change of medication or augmentation can be performed depending upon level of response. This process is repeated at weeks 24 and 36 at which time additional augmentation strategies are allowed. The

objective is to provide active treatment with careful monitoring of depressive symptoms using remission as the goal. For additional medication and algorithm information see Appendix 2. Due to the known side effect profiles of these medications, ECGs and blood tests will be performed in the study as deemed necessary by clinician judgment.

Table 2. Assessment Schedule (Baseline + 13 assessments)

Instrument	Respondent	Wk 0	Wk 4 – 48	Wk 52	Time
2-SRSD	Caregiver	X			3 min
SCID	Caregiver	X			45-60 min

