3.4. Statistical Analyses

Aim 1. Determine if improvement in depressive symptoms in caregivers of children with asthma predicts subsequent improvement in the child's asthma control. A CLPM for longitudinal data will be fit using a maximum likelihood SEM in order to explore reciprocal causation between asthma outcomes and depressive symptoms with lagged effect. A separate model will be constructed for each asthma outcome (e.g. CASI, ACT, steroid bursts). The full CLPM with all cross-lagged paths will test if both the asthma outcomes and depressive symptoms predict each other at subsequent visits. For each full model, paths will connect the value of the depressive symptom score (e.g. HRSD) at each visit to the asthma outcome (e.g. CASI) at each subsequent visit (e.g. 4 weeks later, 8 weeks later). Another set of paths will connect the asthma outcome at each visit to the HRSD at each subsequent visit. The full model will be compared to reduced models containing either the first set of paths or the second set. We hypothesize that the model with the first set of paths will provide a better fit than the second set. The models will be compared on goodness of fit criteria, a non-significant X^2 p-value .05 or more, fit indices .90 or more, RMSEA .05 or less, and significant path coefficients.⁶⁸⁻⁷⁵ Extensive overviews of the use of this CLPM for longitudinal data analyses are given by Cole and Maxwell and MacKinnon.^{70, 75} We will follow Cole and Maxwell's⁷⁰ guidelines for testing the proposed causal relationship, caregivers' depressive symptoms preceding child's asthma outcomes, with longitudinal data using SEM software *Mplus*. We will control for variables that might impact depressive symptoms or asthma response including age, gender and race/ethnicity. The primary analysis for this aim will use CASI scores for the child and caregiver HRSD scores. The HRSD is a widely used clinician-rated depression scale while the CASI scores take into account both asthma symptoms and asthma medication use to treat symptoms. Similar analysis will be conducted using the QIDS-SR as the depression measure and STAI as a caregiver anxiety measure. ACT scores and steroid bursts will be used as well as CASI scores in the analysis.

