Power: No data exist on which to base a power analysis. However, the hypothesis tests used here involve testing regression coefficients. To obtain an approximate idea of the power of our tests, we can refer to the test of a regression coefficient that can be detected with 80% power given a sample of 175. If we conservatively assume 10 predictors for the Primary Aim and Secondary Aim 2, then an effect size of $f^2 = 0.10$ could be detected. This effect size is classified as small ($f^2 = 0.02$) to medium ($f^2 = 0.15$) according to Cohen.⁶⁹ In the full model for Secondary Aims 1, 2 and 3 there are 13 measurement occasions and approximately 200 paths; however, the hypotheses to be tested involve the 78 paths between each visit and each later visit. Given this number of predictors to be tested, an effect size of 0.31 could be detected with 80% power. This effect size is classified as medium ($f^2 = 0.15$) to large ($f^2 = 0.35$) according to Cohen.⁶⁹

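### With 26 to 28 repeated measures in fewer than 200 families, the uncorrected chi-square criterion and the full-versus-reduced comparison in Aim 1 do not hold their nominal 5%; a small-sample correction is needed.

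*Combined protocol and SAP*

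**What the plan says.** Section 3.4, Aim 1, sets out the model: "A CLPM for longitudinal data will be fit using a maximum likelihood SEM in order to explore reciprocal causation". The first set of paths is: "paths will connect the value of the depressive symptom score (e.g. HRSD) at each visit to the asthma outcome (e.g. CASI) at each subsequent visit". The reverse direction follows: "Another set of paths will connect the asthma outcome at each visit to the HRSD at each subsequent visit". The full model is then compared with reduced models that keep only one of the two sets. The criteria are a chi-square p-value of at least .05, followed by "fit indices .90 or more, RMSEA .05 or less, and significant path coefficients". HRSD and CASI form the primary pair. Age, gender and race/ethnicity are controlled for.

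The Power paragraph of the same section counts the model as follows: "there are 13 measurement occasions and approximately 200 paths; however, the hypotheses to be tested involve the 78 paths". The sample size enters as "we can refer to the test of a regression coefficient that can be detected with 80% power given a sample of 175". Section 3.3.c.ii adds: "we propose enrolling 196 participants, rather than the 175 needed based on a power analysis, to allow for some early attrition". Table 2 gives one more occasion than the Power paragraph: "Assessment Schedule (Baseline + 13 assessments".

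Aim 3 reuses the Aim 1 approach for quality of life, and Aim 4 reuses it for both legs of the mediation chain. The plan mentions no small-sample correction, no equality constraint across visits, and no rule for the case where the fit criteria disagree.

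**The concern.** The maximum likelihood chi-square and the likelihood-ratio test have their nominal error rates only in large samples. Here each family contributes 26 to 28 repeated measures, and there are 175 to 196 families. Under these conditions the statistics tend to run above their reference distribution. A correct model then fails the chi-square criterion too often, and a joint test of many cross-lagged paths finds an effect too often when there is none.

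This bears on the primary analysis of Aim 1 and on the models of Aims 3 and 4 built the same way. The evidence that caregiver depression precedes child asthma change rests on these comparisons. The hypothesis is also spread over 78 to 91 coefficients and not stated as one effect.

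**Working it through.** **Inputs.** From section 3.4: 13 occasions, 78 tested paths, N = 175, maximum likelihood, chi-square p of at least .05. From section 3.3.c.ii: enrolment of 196, and retention in an earlier algorithm study of 100%, 99.5%, 83.2% and 75.9% at 3, 6, 9 and 12 months. From Table 2: 14 occasions. Assumed, because the documents do not give them: normal data, autoregression 0.6 (0.3 and 0.8 changed the rates by about 1 point), residual correlation 0.3, and 3 to 5 covariate columns.

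**The plan's own power figures.** These use the overall regression F test with noncentrality f² × N and alpha 0.05 (assumed).
- 78 predictors: residual df = 175 − 78 − 1 = 96, noncentrality 0.31 × 175 = 54.25, power 0.802.
- 10 predictors: residual df = 164, noncentrality 0.10 × 175 = 17.5, power 0.810.

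Both figures reproduce, so the 78 paths were powered as one joint test. That F test holds 5% exactly; the SEM likelihood-ratio test does not.

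**Size of the full model (lag-1 autoregression, without means).**
- 13 occasions: 2 × 78 = 156 cross-paths + 24 autoregressive + 26 variances + 13 covariances = 219. Sample moments 26 × 27 / 2 = 351, so df = 351 − 219 = 132.
- 14 occasions: 182 + 26 + 28 + 14 = 250. Moments 28 × 29 / 2 = 406, so df = 156.

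**Simulated rejection rates when the model is correct and the HRSD-to-CASI paths are zero** (1,200 to 1,500 runs per row, 600 at N = 1000; nominal 5%):

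| Setting | Chi-square | Joint path test |
|---|---|---|
| 13 visits, N = 175, complete | 19.3% | 8.9% |
| 13 visits, N = 196, complete | 17.3% | 8.9% |
| 14 visits, N = 175, complete | 23.1% | 10.4% |
| 13 visits, N = 175, quoted retention | 25.1% | 10.8% |
| 13 visits, N = 196, quoted retention | 20.7% | 10.5% |
| 13 visits, N = 175, 3 covariate columns | 22.3% | 11.9% |
| 13 visits, N = 175, 5 covariate columns | 28.2% | 14.4% |
| 13 visits, N = 196, 4 columns and dropout | 27.2% | 13.5% |
| 13 visits, N = 1000, complete | 6.7% | 6.8% |

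Smaller sets of 300 to 500 runs with complete data gave 13% to 25% for chi-square and 6% to 12% for the joint test. The rates fall towards 5% at N = 1000, so this is a small-sample effect.

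**Check on the mechanism.** At 13 visits and N = 175 the mean chi-square was 144.7 on 132 df, a ratio of 1.096. The 5% critical value is 159.81, and 159.81 / 1.096 = 145.8. A chi-square on 132 df exceeds 145.8 with probability 0.19, which matches the simulated 19.3%. For the joint test, 81.8 / 78 = 1.049, and 99.62 / 1.049 = 95.0, which is exceeded with probability 0.09.

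**Is the parameter count the cause?** Chi-square rejection with complete data and N = 175:
- 13 visits: 219 parameters 19%, 87-parameter lag-1 model 22%.
- 14 visits: 250 parameters 25%, 159-parameter one-direction model 24% to 26%, 94-parameter lag-1 model 29%, 46-parameter equal-path lag-1 model 28%.

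Models with fewer parameters than families over-reject just as often, so the count is not the cause.

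**Does a correction work?** At 14 visits the Swain correction took the full model from 25% to 8% (N = 175) and from 17% to 5% (N = 196). The equal-path lag-1 model went from 28% to 7% and from 21% to 7%. For the 13-visit full model at N = 175 the Swain factor is 0.932. Then 144.7 × 0.932 = 134.8 against 132 df, which implies a rejection rate of about 7%.

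**Single-coefficient test.** One lag-1 HRSD-to-CASI path held equal across visits rejected a true null in 4% to 6% of runs.

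**The case against.** The strongest reply is that chi-square is only one of four listed criteria, and nothing says a model is discarded on chi-square alone. This stands. RMSEA of .05 or less was met in at least 99% of runs, so a reader who inferred that the plan would throw out a correct model one time in four would go beyond the text. What follows is that chi-square and RMSEA will often disagree about a correct model, and the plan does not say what happens then.

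A reader might also infer that a model with more parameters than families is invalid or cannot be estimated. The documents do not support that: the full model is identified, with positive degrees of freedom, and the lean-model results show that the count does not drive the over-rejection.

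A third tempting inference is that small-sample error tilts the result towards the hypothesis. The stated hypothesis compares the first-set with the second-set model. These have equal degrees of freedom and are inflated alike. With neither set of paths present, the first-set model fitted better in 47% to 52% of runs, so no such tilt was found.

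Finally, the plan names no likelihood-ratio test. It is the natural reading of the full-versus-reduced comparison and of the 78-path power figure, but it is an inference. The all-lags design is also deliberate: the Aim 1 text allows effects 4 or 8 weeks later, and section 3.5 expects that asthma control may respond slowly.

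**Conclusion.** The concern holds in this form: the uncorrected chi-square criterion rejects a correct full model in about 13% to 25% of complete-data runs, against a nominal 5%. With the quoted retention the rate is 21% to 25%, and with covariates 22% to 28%. A joint likelihood-ratio test of the HRSD-to-CASI paths runs at about 10%, rising to 12% to 14% with covariates. The reason is 26 to 28 repeated measures set against 175 to 196 families.

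These figures rest on normal data and on the assumed correlations and covariate columns; non-normal outcomes were not simulated. The joint-test figure also rests on reading the comparison as a likelihood-ratio test. The plan's power figures are arithmetically right. The point warrants a change because it touches the primary Aim 1 analysis and is inexpensive to put right.

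**What to change.** 1. In section 3.4, Aim 1, replace the uncorrected chi-square with a small-sample-corrected one (for example Swain) for every cross-lagged model, including those of Aims 3 and 4. Take the full-versus-reduced comparison from a corrected likelihood-ratio test or one calibrated by parametric bootstrap. State how disagreement between the fit criteria will be resolved. This costs SAP wording and some computing.

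2. Recommended: name one primary HRSD-to-CASI test, such as the cross-lagged coefficient held equal across visits in a lag-1 model. Keep a lag-2 model and the all-lags model as sensitivity analyses so that delayed effects are still examined. The downside is that the primary test assumes the same effect at every visit and gives up direct longer-lag effects. Both can be checked by relaxing the constraints. Constraining paths does not cure the chi-square problem, so item 1 is needed either way.

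3. Reconcile the 13 occasions in the Power paragraph with the baseline plus 13 assessments in Table 2. Also reconcile the aim labels: the Power paragraph assigns the 13-occasion model to Secondary Aims 1, 2 and 3, whereas the analysis text describes it under Aim 1.

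### The detectable effect of 0.31 belongs to a single regression with 78 predictors, which the cross-lagged analysis never fits; the figure is too large on every reading examined

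*Combined protocol and SAP*

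**What the plan says.** The Power paragraph of Section 3.4 says that no data exist for a power analysis. It offers an approximate guide instead: "we can refer to the test of a regression coefficient that can be detected with 80% power given a sample of 175". With 10 predictors it gives f² = 0.10. For the cross-lagged models it notes that "there are 13 measurement occasions and approximately 200 paths" and that "the hypotheses to be tested involve the 78 paths between each visit and each later visit". It then concludes: "Given this number of predictors to be tested, an effect size of 0.31 could be detected with 80% power". It places this value between Cohen's medium (0.15) and large (0.35).

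The model itself is described under Aim 1 in the same section: "paths will connect the value of the depressive symptom score (e.g. HRSD) at each visit to the asthma outcome (e.g. CASI") at each subsequent visit, with a second set of paths in the other direction. On testing, it says: "The full model will be compared to reduced models containing either the first set of paths or the second set". The models are judged on overall chi-square, fit indices, RMSEA and the significance of path coefficients.

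**The concern.** A detectable f² has meaning only for a stated test in a stated equation. The sentence treats all 78 paths as predictors of one outcome in one regression. In a cross-lagged model the asthma score at each occasion has its own equation, and only earlier depression scores enter it. The 78 paths are therefore a sum over equations. The paragraph also says that it powers the test of a coefficient, and then gives the result of a 78-df overall test.

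What is at stake is how results will be read. This is the only sensitivity statement tied to the path structure of the cross-lagged analyses. As written, it tells readers that only medium-to-large effects could be found. A null result could then be dismissed as uninformative about smaller effects that the design could in fact detect.

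**Working it through.** **Inputs.** From the Power paragraph: n = 175, power 80%, 78 paths, 13 occasions. Alpha is not given there, so 0.05 is assumed; the nearest figure in Section 3.4 is a model-fit criterion ("a non-significant X^2 p-value .05 or more"), not a test level. All figures below take 175 complete cases unless stated otherwise.

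**1. Reproducing 0.31.** Overall F test in one regression: u = 78, v = 175 − 78 − 1 = 96, noncentrality λ = f² × 175.
- 80% power needs f² = 0.309; at f² = 0.31 the power is 80.2%.
- The same formula with u = 10 gives 0.098, matching the companion figure of 0.10.
- Variants that do not give 0.31: alpha 0.01, 0.025 or 0.10 (0.424, 0.360, 0.254); n = 196 (0.260); a 1-df test of one coefficient among 78 predictors (0.046).

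**2. Where the 78 paths are.** The asthma score at occasion k has k − 1 earlier depression scores. Over occasions 2 to 13 this is 1 + 2 + … + 12 = 13 × 12 / 2 = 78 paths in 12 equations. No equation holds more than 12 of them.

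**3. Detectable f² under the tests that the text could mean.**

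| Test | Detectable f² | 0.31 divided by it |
|---|---|---|
| One path, alpha 0.05 | 0.045 | 6.8 |
| One path, alpha/78 | 0.107 | 2.9 |
| One equation, 1 to 12 paths jointly, alpha 0.05 | 0.045 to 0.106 | 6.8 to 2.9 |
| One equation, alpha/12 | 0.08 to 0.17 | 3.9 to 1.8 |
| Joint 78-df test, total effect | 0.21 to 0.23 | 1.5 to 1.3 |

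Other predictors in the same equation hardly matter: for 12 paths the value is 0.1056 without them and 0.1062 with 15 others.

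**4. The joint test.** With 78 df and alpha 0.05, 80% power needs noncentrality 36.43.
- Total: 36.43 / 175 = 0.208. If the effect is all in one equation, on the log scale, exp(0.208) − 1 = 0.231.
- Equal in all 12 equations: 36.43 / (12 × 175) = 0.0173 each, or 0.0175 on the log scale.

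**5. Small-sample check of the joint test.** Simulation with 12 independent equations, the j-th holding 2j + 3 predictors, and 175 families:
- The ordinary chi-square cutoff (99.6) has about 17% type I error. With only one autoregressive term and four covariates per equation besides the tested paths, it is about 11%.
- With a calibrated cutoff (about 111), power is 78% at f² = 0.0175 per equation and 79% at 0.018.
- Section 3.3.c.ii cites 75.9% retention at 12 months in an earlier algorithm study: 0.759 × 196 ≈ 149. If every equation had 149 families, calibrated power at 0.0175 is about 67%.

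**6. Number of occasions.** The schedule is headed "Table 2. Assessment Schedule (Baseline + 13 assessments"), which makes 14 occasions, 14 × 13 / 2 = 91 paths and 13 equations. The joint test then needs noncentrality 38.93: 0.25 if all in one equation, and 38.93 / (13 × 175) = 0.0171 each if equal. The conclusion is unchanged.

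**The case against.** The plan calls its calculation approximate and says that it has no data to build on. The error is on the safe side: it understates sensitivity, so no family is enrolled in vain because of it. On a like-for-like comparison of totals, 0.31 is only 1.3 to 1.5 times the joint-test value. All of this stands, and it limits the weight of the point. It does not rescue the figure, because being approximate does not make an f² from a model that is not fitted describe one that is.

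A reader might infer that 0.31 is about 18 times too large per equation (0.31 / 0.0173 = 17.9). The documents do not support that as a general statement. The 0.0173 is an equal one-twelfth share of a joint effect, not what one equation can detect. At f² = 0.0175 with 175 families, power is about 41% for a one-path equation, 20% for six paths and 15% for twelve. The ratio also presupposes a 78-df joint test. Dropping one set of paths from the full model would produce such a test, but Section 3.4 never names it. The section lists significant path coefficients among its criteria, and the two reduced models are not nested in each other.

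Nor can one say that the sentence misstates the power of the primary analysis. The paragraph attaches 0.31 to Secondary Aims 1, 2 and 3 and gives the Primary Aim the 0.10 figure. Those labels do not map cleanly onto Aims 1 to 4.

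**Conclusion.** The sentence is wrong as written. The 0.31 is the overall f² of a 78-predictor regression that is not part of the plan, and its medium-to-large label falls with it. It exceeds the detectable effect by a factor of about 3 to 7 for one path or one equation at unadjusted alpha, and of about 1.3 to 1.5 for the total effect in a joint test. No single corrected number follows from the documents, because they do not say which test is powered or at what alpha. The sizes rest on alpha 0.05 and 175 complete cases; the joint-test values are also large-sample figures.

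This is a misspecified power statement, not evidence that the trial is too small.

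**What to change.** In the Power paragraph of Section 3.4:
- Name the test that is powered (single path, one equation's lagged paths, or the joint set) and its alpha, including any adjustment for the number of paths or equations.
- Replace the 0.31 sentence and its label with the detectable effect for that test. For example: f² of about 0.05 to 0.11 per visit equation at unadjusted alpha 0.05 with 175 complete cases.
- If the joint test is meant, report it separately as a total of about 0.21 to 0.23, and say that 0.017 per equation holds only if the effect is equal in all 12.
- Take the final figure from a short Mplus Monte Carlo run of the planned model that allows for dropout. For the joint test, use a calibrated cutoff, because the uncorrected chi-square cutoff inflates type I error at this sample size.

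The cost is a few sentences and a short simulation. The sample size does not change.
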